Study Title: Antidepressant Response in the Treatment of Depressive Symptoms and Frailty Characteristics in Older Adults

Document Date: 11/9/2012

NCT: 01973283

Statistical Analyses:

The data analyses utilize linear mixed effects regression since this approach can handle missing data and the correlation of repeated measurements within the individual. Mixed effects models using maximum likelihood estimation provide valid inferences in the presence of ignorable nonresponse. I will be trained by [name] to use Supermix software written by Donald Hedeker and Robert Gibbons for the analysis of longitudinal data using mixed-effects linear regression. To test Hypothesis 1, I will use linear mixed effects regression of depression score across time as a function of frailty deficit group (those with specific frailty deficits=1, those without deficits=0), 3 time dummy variables (time1=1 for week 8 and 0 otherwise, time2=1 for 6 months and 0 otherwise and time3=1 for 12 months and 0 otherwise) and the interaction of group by time dummies, with a random effect for repeated measures within the individual. I will use a contrast within this model to estimate and test the significance of the difference in outcomes between those with and without deficits at the end of the Acute Phase (8 or 16 weeks). Hypotheses 2 (outcome: total frailty characteristics) and 3 (outcomes: WHODAS2.0, SPPB, ECog, actigraphy scores; IL-6, CRP, serum albumin levels) will be tested in a similar way. The contrasts to test Hypothesis 3 will evaluate the deficit vs. non-deficit differences at 6 months and at 12 months (end of the Follow-up). The relationship between baseline impairment in domains of cognition and frailty characteristics will also be explored.

The power analysis for Aim 1 and Aim 2 is based upon the calculations for longitudinal models given by Hedeker and colleagues, with 4-time points assumed (0, 8 weeks, 6 months and 12 months) for the trend line. A two-group design and a random-effects structure with random slope, residual term and autocorrelated residuals, ICC=0.3 and a 5% attrition rate between each pair of assessments are assumed. Tests are 2-tailed with $\alpha = .05$. To test a between groups linear trend effect, 30 subjects per group at baseline will provide sufficient power to test for a moderate effect (a between groups difference increasing linearly from 0 at baseline to .6 SD units). I recognize the limitations of using pilot studies to guide power calculations for future R01. The proposed study however will be sufficiently powered to determine whether the effect size is clinically meaningful, i.e. an effect size that is somewhat larger than moderate is likely to be clinically meaningful.

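### The contrasts rest on maximum likelihood with no stated small-sample correction, so at 30 per group standard errors are about 1.7% too small and the .05 tests are slightly liberal

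*SAP*

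**What the plan says.** The first paragraph of the SAP's Statistical Analyses section chooses linear mixed-effects regression for all three hypotheses. The only estimation method it names is ML, supported by the statement that "Mixed effects models using maximum likelihood estimation provide valid inferences in the presence of ignorable nonresponse". The model contains a group indicator, three time dummies "and the interaction of group by time dummies, with a random effect for repeated measures within the individual". Hypothesis 1 is tested by a between-group contrast from this model, and Hypotheses 2 and 3 follow the same approach.

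The power paragraph, which covers Aims 1 and 2, sets two-tailed tests at .05 and "30 subjects per group at baseline". It also says that "ICC=0.3 and a 5% attrition rate between each pair of assessments are assumed".

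The section does not mention REML or a degrees-of-freedom method, and does not say whether contrasts are referred to a normal or a t distribution.

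**The concern.** ML estimates variances as if the fitted means were known. In a large trial this is harmless. With 60 people and eight fitted means, the variances come out systematically low, even when the covariance structure is exactly right. Standard errors are then too small, confidence intervals too narrow and p-values too low, always in the same direction. The reason given for ML is its behaviour under ignorable nonresponse. That does not favour ML over REML, which is also likelihood-based and keeps the same protection. What is at stake is whether the stated two-tailed .05 is the error rate actually delivered.

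**Working it through.** **Inputs from the SAP.** 30 per group, so N = 60; 4 time points; 2 groups × 4 visits = 8 fitted means; ICC 0.3; 5% loss per interval; two-tailed .05.

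**Assumptions.** The covariance is a correctly specified random intercept, the groups are of equal size, and the total variance is set to 1. The closed form takes complete data; dropout enters through simulation. The power paragraph also mentions a random slope and autocorrelated residuals but gives no values for them.

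**The plan's own figure.** The figure to check is the nominal .05. In this balanced case, REML with a t reference on matching degrees of freedom returns it.

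**Step 1: variance ratio.** The between-person sum of squares has 60 − 2 = 58 degrees of freedom, and the within-person one has 60 × 3 − 6 = 174. ML divides them by 60 and 180. Both ratios are equal: 58/60 = 174/180 = 0.967. Every variance built from these two mean squares is therefore 0.967 of its REML value. Standard errors are √0.967 = 0.983 of theirs, or 1.7% too small.

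**Step 2: degrees of freedom for a single-visit contrast.** The between-person mean square has expectation 0.7 + 4 × 0.3 = 1.9, and the within-person one 0.7. The single-visit variance is 1.9/4 + 0.75 × 0.7 = 0.475 + 0.525 = 1. The Satterthwaite value is 1 / (0.475²/58 + 0.525²/174) = 183. The floor is 58, reached as the ICC approaches 1 or if the visit is analysed alone.

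**Step 3: true error.** This is 2 × P(t > c × k), where c is the critical value used and k is 0.983 for ML or 1 for REML.

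| Estimation and reference | True error, 183 df | True error, 58 df |
|---|---|---|
| REML, t on matching df | 5.0% | 5.0% |
| REML, normal | 5.15% | 5.5% |
| ML, t on matching df | 5.4% | 5.4% |
| ML, normal | 5.55% | 5.9% |
| ML, t on 58 df | 5.06% | 5.4% |

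The ML bias alone moves 5.0% to 5.4%. Anything beyond that comes from using a normal reference in place of t.

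**Step 4: simulation with dropout.** In 5,000 null trials at 30/30 with 5% loss per interval (Monte Carlo standard error 0.3 points), ML with a normal reference rejected in 5.8% at both week 8 and month 12. REML with a normal reference gave 5.4% and 5.3%. REML with t on 58 df gave 4.8% at both. The simulated ratio of ML to REML standard errors was 0.982, which agrees with Step 1. A 15/45 split gave the same ratio. Its ML rejection rates (6.5% at week 8, 4.9% at month 12; 3,000 runs, Monte Carlo standard error 0.4 points) are too noisy to add more.

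**Step 5: effect on reported results (ML with a normal reference).** Coverage is about 94.1 to 94.4%. Intervals are 2.3 to 3.7% too narrow. A correct p of .05 would be reported as about .042 to .045.

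**Step 6: other sample sizes.** With ML and a normal reference, N = 40 gives 5.8 to 6.4% and N = 80 gives 5.4 to 5.7%.

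**The case against.** The strongest reply is that the SAP makes no false statement here. The sentence about ML concerns missing data and is correct; it claims nothing about small samples. This stands, so the point is about the method adopted at this sample size, not about an error in that sentence.

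A second reply is that the size depends on a reference distribution that the SAP does not give. This also stands. At ICC 0.3, ML with t on 58 df is close to nominal at 5.06%. A reader might infer that every contrast will reject too often by nearly a full point, but the document supports that only if a normal reference is used and the effective degrees of freedom are near 58.

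A third reply is that the sample size is given for Aims 1 and 2 only. A reader might carry N = 60 over to Hypothesis 3; the document does not say so, and for that hypothesis it is an assumption.

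Two further inferences should not be drawn:

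- **That the variance bias grows with a richer covariance model.** With complete data and group-by-visit means, an unstructured ML covariance is also exactly 58/60 of the unbiased one. What changes is the effective degrees of freedom. In any case, the analysis paragraph specifies a random effect within the individual and not an unstructured covariance.
- **That the bias would matter for planning a later study.** An SD understated by 1.7% is small beside its own sampling error of about 1/√(2 × 58) = 9%, and the SAP already acknowledges the limits of pilot data for that purpose.

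**Conclusion.** The point holds as a minor one. As written, the plan gives standard errors about 1.7% too small. The true two-sided error is about 5.4% from ML alone, and about 5.55 to 5.9% if a normal reference is used as well. The direction is always towards significance, but only a borderline result could change.

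This rests on 30 per group, a mean model saturated in group by time, a correctly specified random intercept, and ML being used for every contrast. The last is inferred from ML being the only method named and from the shared approach across hypotheses. For Hypothesis 3 it also rests on a similar sample size.

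**What to change.** State in the Statistical Analyses section that the Hypothesis 1 to 3 contrasts and their confidence intervals are estimated by REML, with t tests on Kenward-Roger or Satterthwaite degrees of freedom. ML can be kept for comparing models with different mean structures. If the named package does not offer this, run the contrasts in another standard mixed-model procedure that does. The existing argument about ignorable nonresponse carries over unchanged.

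The cost is one sentence, possibly a second package, and slightly wider intervals. No extra data or participants are needed.

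### The H1 and H3 contrasts are worded as group differences at a visit, so they include any baseline gap; the power paragraph describes a different test, and week 16 has no time code

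*SAP*

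**What the plan says.** All of this is in the SAP, under Statistical Analyses and in the power paragraph that follows.

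- **Groups.** The comparison variable is "frailty deficit group (those with specific frailty deficits=1, those without deficits=0".
- **Model.** A mixed model has group, three time dummies, their interactions with group, and a random effect for the individual. The dummies are "time1=1 for week 8 and 0 otherwise, time2=1 for 6 months and 0 otherwise and time3=1 for 12 months and 0 otherwise".
- **Hypothesis 1 (depression score).** A contrast in this model will "test the significance of the difference in outcomes between those with and without deficits at the end of the Acute Phase", which is given as either week 8 or week 16.
- **Hypothesis 2.** It is to be tested similarly, with no contrast of its own described.
- **Hypothesis 3 (function, cognition, actigraphy, blood markers).** The contrasts "evaluate the deficit vs. non-deficit differences at 6 months and at 12 months".
- **Power.** The calculation covers Aims 1 and 2, "with 4-time points assumed (0, 8 weeks, 6 months and 12 months) for the trend line". It takes 30 per group as enough for "a between groups difference increasing linearly from 0 at baseline to .6 SD units". It assumes an ICC of 0.3, 5% attrition between assessments and two-sided testing at 0.05. No power percentage is given.

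**The concern.** The groups are defined by a participant characteristic, so nothing in the design makes them equal at baseline. A difference at a follow-up visit then mixes two things: the gap the groups started with, and any difference in how they changed. If the hypotheses concern response to treatment, the contrast as worded could be significant when both groups improved equally. If they concern level, the same result is a true difference but says nothing about response.

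The power statement does not help the reader choose. It belongs to a slope comparison over the whole follow-up, while the analysis paragraph tests single visits.

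The week-16 gap is a separate, purely textual matter. The Acute Phase contrast has no corresponding model term if the phase ends at week 16.

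**Working it through.** **1. What the worded contrast estimates.** With every dummy at 0 for baseline, the expected group difference is:

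- baseline: group
- week 8: group + group×time1
- 6 months: group + group×time2
- 12 months: group + group×time3

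The group coefficient is the baseline gap. The difference in change from baseline is the interaction coefficient alone.

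**2. Week 16.** Each dummy is 0 except at its own visit, and none belongs to week 16. A separate week-16 record would have all three at 0, which is the baseline code. The power calculation has no week-16 visit either.

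**3. The plan's own power figure.** It is a sample size without a stated power, so it cannot be reproduced exactly. Using total SD 1, constant correlation 0.3 and n per group of 30 × 0.95^k at visit k, the trend test is z = c′d / √(c′Vc), where V has elements 2 × correlation / √(n_j n_k).

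- Visits equally spaced: c = (−1.5, −0.5, 0.5, 1.5), d = (0, 0.2, 0.4, 0.6), c′d = 1.0, √(c′Vc) = 0.503, z = 1.99, power about 51%.
- Visits at weeks 0, 8, 26 and 52: power about 53%.

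The SAP gives no values for its random slope or autocorrelation, and these move the result. What matters here is that the calculation is for a trend across four visits.

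**4. What that line implies at week 8.** In calendar time, 0.6 × 8/52 = 0.09 SD. With equally spaced visits, 0.6/3 = 0.20 SD.

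**5. Standard errors at single visits.** SE(level) = √(2/n) and SE(change) = √(4(1 − r)/n), with r = 0.3.

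| Visit | n per group | SE level | SE change |
|---|---|---|---|
| Week 8 | 28.5 | 0.265 | 0.313 |
| 6 months | 27.1 | 0.272 | 0.322 |
| 12 months | 25.7 | 0.279 | 0.330 |

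On the line in step 4, with no baseline gap, week-8 power is 6% to 12% for level and 6% to 10% for change.

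**6. Illustration of a baseline gap.** The SAP gives no gap, so a range is assumed. Both groups change equally and the gap d persists. The probability of significance is P(|Z + d/SE| > 1.96). At week 8 with d = 0.5, d/SE = 0.5/0.265 = 1.89, giving 47%.

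| Visit | gap 0.3 SD | gap 0.5 SD | gap 0.8 SD | change contrast |
|---|---|---|---|---|
| Week 8 | 20% | 47% | 86% | 5% |
| 6 months | 20% | 45% | 84% | 5% |
| 12 months | 19% | 43% | 82% | 5% |

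**7. Precision cost of a change contrast.** The difference detectable with 80% power is (1.96 + 0.84) × SE = 2.80 × SE.

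- Week 8: 0.74 SD for level, 0.88 SD for change.
- 12 months: 0.78 SD for level, 0.92 SD for change.
- Week-8 change contrast at r = 0.5: 0.74 SD, so no loss. At r = 0.7: 0.57 SD, a gain.

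Generalised least squares using all visits with dropout gives similar values at r = 0.3: 0.74 and 0.87 SD at week 8, 0.77 and 0.90 SD at 12 months.

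**The case against.** The strongest reply is that this is an ambiguity and not a demonstrated error. The hypotheses are not stated in the SAP. If Hypothesis 1 is about how depressed each group remains when the Acute Phase ends, the worded contrast is the right one. The model also contains the group-by-time terms, and no contrast coefficients are listed, so a change contrast may be intended. This stands: a reader might infer that the plan has chosen the wrong contrast, and the SAP does not support that. What remains is that two analysts could test different quantities from the same text.

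The rejection rates can also be over-read as false-positive rates. They depend on an assumed gap, and they are errors only if change is the target; under a level reading they are power. The SAP's only statement about baseline is the planning assumption of no difference. Under it, level and change have the same expected value and, at ICC 0.3, the level contrast is the more precise. But that assumption sits in the power paragraph, and nothing in the analysis secures it.

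A reader might infer that Hypothesis 1 has only 6% to 12% power. That goes too far. Matching Aim 1 to Hypothesis 1 is an inference, and the 0.09 to 0.20 SD is read off a line stated for the trend test, not given as the expected week-8 effect. If 0.6 SD were present at week 8, the level contrast would have about 62% power (0.6/0.265 = 2.26).

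The change contrast is not free of difficulty either. If grouping depends on a baseline measure related to the outcome, regression to the mean can make changes differ without any difference in response.

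The week-16 miscoding arises only if a separate week-16 record enters the model, which the SAP does not say. The mismatch between the two possible phase ends and the dummies remains in any case.

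**Conclusion.** The point holds as a matter of specification and should be fixed.

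- **Contrast.** As worded, the Hypothesis 1 and 3 contrasts are differences in level between groups defined by frailty deficits. They include any baseline gap and cannot alone show different response. Whether level or change is intended is not settled by the SAP.
- **Power.** The claim that 30 per group is enough belongs to a four-visit linear trend starting from no difference. The analysis paragraph does not specify that test, so the claim does not describe the single-visit contrasts. Step 3 might be read as showing that the trial is underpowered for its own trend; without a target power, slope variance or autocorrelation, the SAP does not allow that conclusion.
- **Week 16.** "at the end of the Acute Phase (8 or 16 weeks") and the time dummies do not agree.

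The 20%, 47% and 86% at week 8 are an illustration. They assume gaps of 0.3, 0.5 and 0.8 SD, equal change in both groups, and the SAP's sample size and attrition. The change-contrast precision further assumes constant correlation, as a single random effect implies.

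Hypothesis 2 is tested similarly, so it needs the same clarification. A reader might infer that its outcome overlaps with the group definition, but the SAP does not define either closely enough to establish this.

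**What to change.** 1. State for each hypothesis whether level or change is meant, and write out the contrast coefficients.
2. If response is the question, test the group-by-time coefficient at the Acute Phase visit for Hypothesis 1, and group×time2 and group×time3 for Hypothesis 3. If level is meant, say so and do not interpret a difference as differential response. State the Hypothesis 2 contrast in the same way.
3. Reconcile the two possible Acute Phase ends with the dummies, so that no post-baseline visit carries the baseline code. No view is taken here on which duration is right.
4. Restate the power paragraph for the contrast actually tested, with the correlation assumptions given as numbers.

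The cost is revised wording and a new power calculation on the same data, plus one dummy and its interaction if week 16 is an analysis visit. A change contrast loses precision at ICC 0.3 (about 0.74 to 0.88 SD detectable at week 8), with no loss at a baseline-to-visit correlation of 0.5. If it is chosen, the SAP should also acknowledge possible regression to the mean.

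### The sample-size claim is for a linear trend, but Hypothesis 1 is tested by a single-visit contrast with about 6% to 12% power under that trend

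*SAP*

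**What the plan says.** The power paragraph of the SAP (Statistical Analyses, second paragraph) takes four time points: baseline, 8 weeks, 6 months and 12 months. It states: "To test a between groups linear trend effect, 30 subjects per group at baseline will provide sufficient power to test for a moderate effect". The effect is described as "a between groups difference increasing linearly from 0 at baseline to .6 SD units". The covariance assumptions are "random slope, residual term and autocorrelated residuals, ICC=0.3 and a 5% attrition rate between each pair of assessments", without values for the slope variance or the autocorrelation. Tests are two-sided at 5%. The power itself is called sufficient and is not given as a number.

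The analysis paragraph (Statistical Analyses, first paragraph) has no linear time term. Its model holds group, three visit dummies and the group-by-dummy interactions. Hypothesis 1 is tested by a contrast for the "difference in outcomes between those with and without deficits at the end of the Acute Phase (8 or 16 weeks"). Hypothesis 2 is to be handled similarly, with no visit named. For Hypothesis 3: "The contrasts to test Hypothesis 3 will evaluate the deficit vs. non-deficit differences at 6 months and at 12 months".

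**The concern.** The powered test and the test specified for Hypothesis 1 are different. A trend test draws on all four time points and on a difference that is largest at the last one. The Hypothesis 1 contrast looks at one early visit, where a linearly growing difference is still small. A sample size that suits the first says little about the second.

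This matters because the power sentence is the only support given for 30 per group, and the SAP goes on to describe the study as adequately powered to judge clinical meaningfulness. A non-significant contrast at the end of the Acute Phase could then be taken as evidence from an adequately powered test. Under the plan's own effect model, that test would miss the difference about nine times in ten.

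**Working it through.** **Inputs from the SAP.** 30 per group at baseline; 5% loss per interval; ICC 0.3; two-sided alpha 0.05; difference rising linearly from 0 to 0.6 SD.

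**Assumptions added here.** 0.6 SD is reached at 12 months. The SD is 1 at every visit. Correlation is compound symmetric, because no slope variance or autocorrelation is given. Tests use a normal approximation.

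**1. The plan's own figure.** No power percentage is stated, so none can be reproduced exactly. The trend test can be approximated.
- With no dropout and time scaled 0 to 1, the SE of the slope difference is √[2(1−ρ)/(n·Σ(x−x̄)²)].
- Equal visit steps give Σ(x−x̄)² = 5/9, so SE = √[2×0.7/(30×0.556)] = 0.290. Then 0.6/0.290 = 2.07 and power is 54%. Calendar time gives 57%.
- With 5% loss per interval (generalised least squares over the dropout patterns), power is 50% (equal steps) to 52% (calendar time).
- Other choices at ICC 0.3 give 37% to 51% (assumed autocorrelation or random slope) and 66% to 71% (baseline group difference fixed at 0). No two-sided variant run at ICC 0.3 reached 80%.

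**2. Difference expected at the Hypothesis 1 visit.**
- Week 8, calendar time: 0.6 × 8/52 = 0.092 SD.
- Week 16, calendar time: 0.6 × 16/52 = 0.185 SD.
- First follow-up visit, equal steps: 0.6 × 1/3 = 0.20 SD.

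**3. Precision of that contrast.** Observed per group at week 8: 30 × 0.95 = 28.5. By hand, SE = √(2/28.5) = 0.265; the full model gives 0.264. The week-8 SE is also used for week 16, because the model has no week-16 term.

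**4. Power** = Φ(δ/SE − 1.96) + Φ(−δ/SE − 1.96).

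| Contrast (level difference) | δ (SD) | Power |
|---|---|---|
| Week 8, calendar time | 0.092 | 6% |
| Week 16, calendar time | 0.185 | 11% |
| Week 8, equal steps | 0.20 | 12% |
| Week 8, all of 0.6 SD present | 0.60 | 62% |
| 6 months, calendar time | 0.30 | 20–21% |
| 6 months, equal steps | 0.40 | 32–33% |
| 12 months | 0.60 | 58–61% |

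The difference detectable at week 8 with 80% power is (1.960 + 0.842) × 0.264 = 0.74 SD.

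**5. Sensitivity.**
- For correlations of 0.3 to 0.7, week-8 power under the trend changes by less than 1 point and the detectable difference stays at 0.73 to 0.74 SD.
- Adding a random slope (variance 0.1 to 0.3 at the last visit) moves the detectable difference only to 0.745–0.753 SD.
- If the contrast is read as a difference in change from baseline, the model SE is 0.311, 0.263 and 0.204 at correlations 0.3, 0.5 and 0.7. The 80% detectable difference is then 0.87, 0.74 and 0.57 SD. At ICC 0.3, week-8 power under the trend is 6% (calendar time) to 10% (equal steps).

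**The case against.** Five points can be made for the plan.

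- **The trend is named in the power paragraph and can be formed from the dummy model** as a linear contrast on the interaction coefficients. That is true. But the analysis paragraph never specifies it, and it is not the Hypothesis 1 test.
- **The 6% to 12% range is conditional.** It needs 0.6 SD to be reached at 12 months and the linear path to hold at week 8, whereas the dummy model imposes no linearity. This stands as a caveat. Two results do not depend on it: no power is stated for the planned contrast, and 80% power needs about 0.74 SD. Putting the full 0.6 SD at week 8 gives only about 62%, and that is not a difference growing linearly to 12 months.
- **The power claim refers to Aims 1 and 2, and their mapping to Hypotheses 1 to 3 is not shown.** The weight should therefore rest on Hypothesis 1. The later contrasts are given for information. At 12 months the mismatch does little harm, since 58% is no worse than the 50% to 52% found for the trend.
- **The 50% to 52% for the trend depends on compound symmetry and a free baseline difference.** This is correct, and the wider range of 37% to 71% is shown above. Its upper end requires fixing the baseline difference at 0, which the stated model does not do.
- **The study is presented as a pilot, and the approximation is normal.** The SAP acknowledges the limits of pilots but still claims adequate power. A t reference distribution changes the figures only to about 0.75 SD and 61%.

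**Conclusion.** The concern holds. The claim of sufficient power does not apply to the Hypothesis 1 contrast, and no power is given for any single-visit contrast in the SAP. The mismatch is plain from the text and needs no assumption. Its size rests on the 12-month endpoint for 0.6 SD, which the text implies but does not state. It barely depends on the covariance structure when the contrast is a level difference. It should be fixed, but it does not invalidate the analysis model.

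**What to change.** Choose one of two routes.

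**Keep the contrast as the test.** Replace the trend sentence with the power of the planned contrast and a difference specified for that visit. For example: with 30 per group at baseline and 5% attrition between each pair of assessments, the group contrast at the end of the Acute Phase has 80% power (two-sided alpha 0.05) for about 0.74 SD, and about 62% for 0.6 SD if all of it is present at that visit. If a difference in change from baseline is meant, say so and give the detectable difference by assumed correlation (0.87, 0.74 and 0.57 SD at 0.3, 0.5 and 0.7).

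**Make the trend the test.** Define it in the analysis paragraph as a linear contrast on the three group-by-dummy coefficients, or replace the dummies with linear time. It cannot be added as further terms: the model has 8 columns and is saturated in time, and adding time and group-by-time gives 10 columns of rank 8. Then state numeric power with the slope variance, the autocorrelation and the treatment of the baseline difference.

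The cost is wording and a recalculation. The power statement becomes less favourable; enrolment does not change.
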